### **5.3. Study treatment**

#### **5.3.1. Concomitant Interventions**

Any concomitant Interventions at the intervention area of the study are allowed and must be recorded (date and specify intervention).

### **5.4. Study Duration**

The total study duration is expected to be approximately 2 years, calculated from the inclusion of the first patient to the completion of the 12-month follow-up visit of the last enrolled patient.

For each patient, the individual study participation will last approximately 13 months, including the baseline screening, surgery, and all scheduled follow-up visits up to 12 months post-surgery.

For the purpose of study planning, monitoring, and reporting, the following definitions are applied:

- First Patient First Visit (FPFV): the date on which the first eligible patient undergoes the baseline visit and is enrolled in the study.
- Last Patient First Visit (LPFV): the date on which the last eligible patient undergoes the baseline visit and is enrolled in the study.

- Last Patient Last Visit (LPLV): the date on which the last enrolled patient completes the final (12-month) follow-up visit.
- Final report / evaluation: the period following LPLV during which data cleaning, statistical analysis, and preparation of the final study report are performed.

### 5.5. Discussion of Study Design

This investigation is designed as a post-market clinical follow-up (PMCF) study, since both the test and control interventions (CAF + SCTG with or without adjunctive hyaDENT BG®) are established techniques in periodontal plastic surgery. A prospective, randomized, controlled parallel-arm design was chosen to generate high-level clinical evidence on the adjunctive use of cross-linked hyaluronic acid versus the conventional gold-standard alone. To minimize bias and account for baseline variability, the randomization will be *stratified by recession type* (Cairo RT1 vs RT2 classification), ensuring that defects of differing initial severity are evenly distributed between the test and control groups. Allocation concealment is maintained via sealed, sequentially numbered opaque envelopes, and blinding is upheld for outcome examiners, which together strengthen the internal validity of the trial.

The sample size and power considerations have been tailored to balance scientific rigor with practical feasibility. The trial plans to recruit 34 patients to allow for a ~10% drop-out rate, aiming for 30 patients to complete the 12-month follow-up. This enrollment strategy preserves the statistical power of the study by compensating for potential attrition. The sample size is driven by the primary outcome (complete root coverage at 12 months), which is a critical clinical and esthetic benchmark in mucogingival surgery. Detecting a significant difference in the proportion of sites with complete root coverage between groups will directly address the primary objective and could validate the added value of hyaluronic acid in enhancing surgical outcomes.

In addition to the primary endpoint, the study will evaluate multiple secondary endpoints covering clinical efficacy (such as mean root coverage, CAL gain, and keratinized tissue gain), patient-centered outcomes (pain/discomfort levels and oral health-related quality of life), and esthetic results (RES score). A hierarchical statistical testing plan has been incorporated for these secondary endpoints to allow a confirmatory interpretation of the most relevant

outcomes while controlling the overall Type I error. In practice, this means the analysis will formally test secondary outcomes in a prioritized sequence, enabling the trial to make stronger evidence-based claims about secondary benefits (e.g., improvements in mean root coverage or patient-reported pain) if the data support them. By pre-specifying this hierarchy, the study design addresses multiplicity and increases the reliability of conclusions drawn from secondary analyses.

Overall, the chosen design – including stratified randomization, an adequate sample with drop-out accommodation, and a controlled approach to multiple endpoints – is intended to ensure that the findings are both scientifically robust and applicable to real-world clinical practice. The results of this study will provide valuable clinical data on the potential benefits of adjunctive hyaDENT BG® in periodontal surgery, which can be compared against published outcomes in the literature and used to guide evidence-based decision-making in periodontal therapy.

## **6. MATERIALS AND METHODS**

### **6.1. Study outline**

A prospective, experimental, controlled, randomized study will be performed on 30 patients divided into two groups. In the test group, patients will undergo coronally advanced flap surgery combined with connective tissue graft with application of hyaluronic acid. In the control group, patients will undergo the same surgery without the application of hyaluronic acid.

The study will be complemented by an in vitro component in which a sample of the connective tissue graft will be taken from each patient to isolate fibroblast cells, culture them, and evaluate their viability, proliferation, differentiation, and mediation in cell signaling in the presence or absence of hyaluronic acid.

## **7. CLINICAL TRIAL**

### **7.1. Sample Size and Randomization**

Each patient will be randomly assigned to one of the two study groups (test or control) in a 1:1 ratio. The randomization sequence will be generated using a computer program (e.g., IBM SPSS) with stratification by recession type (Cairo classification RT1 vs RT2) and using permuted

blocks of random sizes. This stratified, blocked randomization ensures that patients with RT1 and RT2 recession defects are equally balanced across the two groups, preventing any imbalance in baseline recession severity. Allocation concealment will be maintained through the use of opaque, sealed, sequentially numbered envelopes. An independent investigator (not involved in the treatment) will open the next envelope in sequence immediately after flap elevation, thereby revealing the group assignment. The treating surgeon will thus be unblinded at the point of graft placement (since they must know whether to apply the HA gel), but the patients will not be explicitly informed of their group allocation. (Patients might potentially guess their group based on postoperative symptoms or the presence of the HA application, so complete patient blinding cannot be guaranteed; however, all outcome assessors remain fully blinded to group assignment.)

Based on the sample size calculations and previous study data, approximately 17 patients per group (34 total) will be enrolled in this trial. This enrollment target includes a buffer for potential drop-outs, with the goal of ending up with at least 15 evaluable patients in each arm at study completion. The groups are defined as follows:

- **Test group (n ≈ 17):** CAF + SCTG with adjunctive hyaDENT BG® (HA applied at the recipient site).
- **Control group (n ≈ 17):** CAF + SCTG without the adjunctive hyaDENT BG® (no HA application).

By employing stratified randomization and concealing the allocation, the study design mitigates selection bias and ensures that both groups are comparable with respect to key prognostic factors (notably the recession type). The 1:1 allocation with an effective sample of ~30 completers (15 per group) provides sufficient power to detect the expected difference in the primary endpoint, while the slight over-enrollment to 34 accounts for attrition and preserves statistical integrity.

## 7.2. Study population

All patients undergoing coronally advanced flap combined with a subepithelial connective tissue graft, at the clinical centre CEPI, Porto, will be screened for this study.

### 7.3. Ethical considerations

The research project will be submitted to the Ethics Committee. All patients signed a written informed consent before participation. The identification of all data is replaced by a code in order to ensure complete confidentiality and anonymity.

### 7.4. Surgical procedure

All patients receive basic periodontal therapy and oral hygiene instructions prior to treatment. The periodontal surgery is performed by a single experienced periodontist. Hyaluronic acid (HA) application is performed by a third examiner who is not involved in the surgical treatment sequence. Surgical chair time was measured using a chronometer from the first incision to the last suture in both groups. Coronally Advanced Flap Combined with a subepithelial connective tissue graft was performed in both patient groups to accomplish root coverage.

#### Surgical technique:

- Local infiltrative anesthesia (2% lidocain with epinephrine at a concentration of 1:100,000)
- Incision design is performed with a microblade (USM-6700) or with a 15c blade
- After flap preparation, a gentle root planing is performed using gracey curettes /mini-five
- Coronal advanced flap is obtained by cutting the superficial muscle fibers using a blade parallel to the external surface of the mucosa.
- Anatomical papillae are de-epithelialized with the scalpel blade and microsurgery scissors.
- The width of the graft was chosen according to the amount of tissue required to cover the exposed root and 3 mm of connective tissue mesial and distal to it.
- Immediately after harvesting, the subepithelial connective tissue graft (SCTG) is placed in a sterile dish
- In the test group, the SCTG is completely immersed (fully soaked) in sterile hyaluronic acid gel
- The graft remains immersed for approximately 1–3 minutes to ensure full surface contact and to prevent dehydration
- Excess hyaluronic acid is allowed to drain passively without compression prior to graft placement

- In the control group, the SCTG is maintained under sterile conditions and hydrated with sterile saline solution for a comparable time interval, without contact with hyaluronic acid

#### **Suture:**

- Suture for connective grafts should be resorbable Vicryl 7-0 with a 6,6 mm P1 needle (3/8 of circumference).
- Suture for the flap is 6-0 resorbable PGA with 11 mm C3 (3/8 circumference) cutting needle or 6-0 resorbable Vicryl with 13 mm C3 (3/8 circumference) cutting needle.

### **7.5. Postoperative protocol**

Post-operative pain and edema were controlled with ibuprofen. Patients received 600 mg at the beginning of the surgical procedure. Subsequent doses were taken only if necessary to control pain. Patients had to record the quantity of analgesics taken during the first week post-surgery.

All patients were instructed to intermittently apply an ice bag on the operated area. Patients were instructed to discontinue tooth brushing and avoid any trauma at the surgical site. A 60-second rinse with 0.12% chlorhexidine digluconate was prescribed twice daily, starting on the third day after surgery, and continued for the first two weeks.

Fourteen days after the surgical treatment, the sutures were removed. Plaque control in the surgically treated area was maintained by chlorhexidine rinsing for an additional 1 week after suture removal. After this period, patients were again instructed in mechanical tooth cleaning of the treated tooth using an ultra-soft toothbrush and a roll technique for 1 month. During this month, chlorhexidine rinsing was used twice a day. Then the patient started to use a soft- toothbrush and chlorhexidine once a day for another month. All patients were recalled for prophylaxis 2 and 4 weeks after suture removal and, subsequently, once every 2 months until the final examination (12 months).

Patients were recalled for follow-up (and professional oral hygiene/maintenance procedures, clinical measurements as needed and photographs) on days 4, 8, 15 and every 2 months until 12 months.

### **7.6. Clinical parameters**

The following clinical measurements are taken at baseline and at 12 months after surgery for each tooth by a blinded calibrated examiner: full-mouth plaque score (FMPS), full-mouth bleeding score (FMBS), bleeding on probing (BOP), probing depth (PD), and clinical attachment level (CAL), using a CP-15 mm graduated periodontal probe.

Photographic recording is done at every visit in order to compare the healing process between the two groups. Photographic record: before treatment, during surgery and follow up at days 4, 8, 15 and every 2 months until 12 months.

Clinical measurements will be performed under standardized clinical conditions (adequate lighting, gentle probing force, and dry field). To ensure measurement standardization and reproducibility, an individualized acrylic stent will be fabricated for each participant to serve as a fixed reference point for all clinical measurements, as described by *Zucchelli et al. 2010* [35]. The stent will be positioned on the occlusal surfaces of adjacent teeth and will include a vertical guiding groove aligned with the mid-buccal aspect of the treated tooth, ensuring consistent probe angulation and insertion point at each timepoint. All measurements will be performed by a single calibrated examiner to eliminate inter-examiner variability and ensure consistency across all study visits.

Prior to the beginning of the study, an intra-examiner calibration process will be performed in order to assess measurement reproducibility. For this purpose, clinical measurements will be recorded in a sample of 10 patients not included in the study population. The same clinical parameters will be reassessed by the same examiner after an interval of approximately 15 days. Intra-examiner reliability will be evaluated by calculating the Cohen's kappa coefficient ( $\kappa$ ) for categorical variables and/or the intraclass correlation coefficient (ICC) for continuous variables, as appropriate. A kappa or ICC value  $\geq 0.75$  will be considered indicative of acceptable intra-examiner agreement. Only after achieving adequate intra-examiner calibration will patient recruitment and data collection for the study commence.

#### **7.6.1. Full-mouth plaque score (FMPS)**

A simplified variant of the Plaque score (Visible Plaque score), proposed by Ainamo and Bay (1975), is used. In this case, the classification criterion is binominal and is based on the presence/absence of plaque on tooth surfaces: 0- Absence of plaque and 1- Presence of visible plaque

Calculation of the Full-mouth plaque score:

$$\text{FMPS(\%)} = \frac{\text{no. of surfaces with plaque}}{\text{nº of surfaces evaluated}} \times 100$$

#### **7.6.2. Full-mouth bleeding score (FMBS)**

For the evaluation of gingival inflammation, a simplified variant, also proposed by Ainamo and Bay (1975), is used. In this case the classification criterion is also binominal: 0- Absence of bleeding and 1- Presence of bleeding from the gingival margin up to 10s after probing

Calculation of the Full-mouth bleeding score:

$$\text{FMBS (\%)} = \frac{\text{no. of surfaces with bleeding}}{\text{no. of evaluated surfaces}} \times 100$$

#### **7.6.3. Gingival recession depth (RD)**

Measured from the CEJ to the most apical extension of the gingival margin using a calibrated UNC-15 periodontal probe, with readings rounded to the nearest 0.5 mm.

#### **7.6.4. Height of keratinized tissue (HKT)**

Measured as the distance (in millimeters) between the gingival margin and the mucogingival junction (MGJ) using a calibrated UNC-15 periodontal probe, with readings rounded to the nearest 0.5 mm.

#### **7.6.5. Probing Depth**

The probing depth is defined as the distance, in millimeters, from the gingival margin to the bottom of the gingival sulcus/pocket. All tooth surfaces (mesio-buccal, centro-buccal, disto-buccal, disto-lingual, centro-lingual and mesio-lingual) are evaluated with a periodontal probe, which is graded every 3 mm. The measurements are recorded to the nearest milimeter. By summing all the PD values it is possible to calculate the average PD value for each patient at the various evaluation times.

#### **7.6.6. Bleeding on probing (BOP)**

Bleeding after probing is a common means of assessing the presence of subgingival inflammation, although its negative predictive value is higher, i.e. when there is no bleeding. In this way, it is possible to check whether a pocket is in its active or inactive state. The measurement is made concurrently with the evaluation of the PD. A simplified variant of the bleeding on probing was proposed by Mühlemann & Son, (1971).

In this case the classification criterion is binominal:

0- Absence of bleeding within 15s;

1- Presence of bleeding from the gingival margin within 15s.

The calculation is obtained by dividing the areas where there was bleeding on probing by the total number of areas evaluated.

#### **7.6.7. Clinical attachment level (CAL)**

The clinical attachment level is defined as the distance in millimeters from the cemento-enamel junction (CEJ) to the bottom of the gingival sulcus or pocket. All tooth surfaces (mesio-buccal, centro-vestibular, disto-buccal, disto-lingual, centro-lingual and mesio-lingual) are evaluated with a periodontal probe, which is graded every 3 mm. The measurements are recorded to the nearest millimeter. By summing all the PD values, it is possible to calculate the average value for each patient at the various evaluation times. The clinical evaluation requires measuring the distance from the free gingival margin to the CEJ.

Thus, the level of insertion can be calculated as follows:

In the presence of gingival recession: Pocket Depth + distance from the gingival margin to the CEJ.

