###### Secondary Hypotheses (H2-H9)

**H2:** Adjunctive hyaDENT BG® leads to greater mean root coverage (MRC) and greater recession reduction (RecRed) at 12 months versus control.

**H3:** Adjunctive hyaDENT BG® yields greater CAL gain and PD reduction compared to control sites at 12 months.

**H4:** Adjunctive hyaDENT BG® results in greater height of keratinized tissue (HKT) gain compared to CAF + SCTG alone.

**H5:** Patients receiving hyaDENT BG® report lower postoperative pain, swelling, and discomfort (VAS)

**H6:** Adjunctive hyaDENT BG® improves oral health–related quality of life, as measured by the OHIP-14 questionnaire at early postoperative time points (3, 5, 14 days, 6 weeks).

**H7:** Adjunctive hyaDENT BG® improves early wound healing score (EHS) at 3, 5, 14 days, and 6 weeks compared to control.

**H8:** Adjunctive hyaDENT BG® provides better aesthetic outcomes (Root Coverage Esthetic Score, RES) compared to CAF + SCTG alone.

**H9:** Adjunctive hyaDENT BG® is associated with a lower incidence of surgical complications (e.g., flap dehiscence, infection, graft necrosis).

Null Hypothesis (H0): No statistically significant differences are observed between test and control groups in any of the evaluated outcomes

Multiplicity Control: To manage the risk of Type I error across multiple endpoints, a hierarchical testing strategy will be applied to the following prioritized hypotheses: H2 (MRC), H3 (CAL and PPD), H4 (HKT), H5 (VAS), and H8 (RES). Each hypothesis in this sequence will be tested at the  $\alpha = 0.05$  level, and testing will proceed only if the previous hypothesis in the hierarchy is statistically significant. Remaining secondary outcomes (H6, H7, H9) will be analyzed descriptively.

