### 5.1.1. Endpoints

#### 5.1.1.1. Primary Endpoint

**Complete Root Coverage (CRC)** at 12 months, defined as the proportion of treated recession sites presenting Recession Depth (RD) = 0 mm relative to the cemento-enamel junction (CEJ). Measurements will be performed with a CP-15 calibrated periodontal probe by a blinded examiner, using the CEJ as a fixed reference point.

Photographic documentation will be standardized using the same digital camera model, lens, and magnification settings. All images will be taken at a fixed distance with the aid of a custom acrylic stent and include a millimeter scale for calibration. Consistent lighting and angulation will be maintained across all time points to ensure reliable visual assessment of root coverage.

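### The measurement site for the H3 outcomes (CAL gain and PD reduction) is unresolved, and the only CAL summary stated is wrongly built from PD values

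*Protocol*

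**What the plan says.** **Surfaces and summary.** For probing depth, Protocol 7.6.5 states: "All tooth surfaces (mesio-buccal, centro-buccal, disto-buccal, disto-lingual, centro-lingual and mesio-lingual) are evaluated with a periodontal probe". It then gives one patient-level summary: "By summing all the PD values it is possible to calculate the average PD value for each patient at the various evaluation times". Section 7.6.7 repeats the six surfaces for CAL and closes with almost the same sentence: "By summing all the PD values, it is possible to calculate the average value for each patient at the various evaluation times". It goes on to give the CAL formula where recession is present: pocket depth plus the distance from the gingival margin to the CEJ.

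**The treated site.** Section 5.2.1 admits patients with a single recession defect. H3 in 4.4.1 says that the test treatment "yields greater CAL gain and PD reduction compared to control sites at 12 months". Section 7.6 describes an individual stent as the reference for all clinical measurements, with "a vertical guiding groove aligned with the mid-buccal aspect of the treated tooth". Section 5.1.1.2 lists CAL gain and PD reduction from baseline to 12 months but names no site.

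**Place in the testing order.** In 4.4.1 the fixed sequence is H2 (MRC), H3 (CAL and PPD), H4 (HKT), H5 (VAS), H8 (RES). Each step is tested only if the one before it is significant.

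**Probes.** For the primary endpoint, 5.1.1.1 says: "Measurements will be performed with a CP-15 calibrated periodontal probe by a blinded examiner". For RD, 7.6.3 says: "using a calibrated UNC-15 periodontal probe, with readings rounded to the nearest 0.5 mm". For PD and CAL, 7.6 names a CP-15 probe, while 7.6.5 and 7.6.7 describe a probe with 3 mm gradations, read to the nearest millimetre.

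**The concern.** There are two separate problems.

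First, the CAL summary in 7.6.7 is wrong as written. It drops the position of the gingival margin, which is the component of CAL that root-coverage surgery is meant to change.

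Second, the protocol points in two directions on what is compared in H3. The single treated recession, the reference to sites and the stent groove suggest one mid-buccal reading per patient. The measurement sections state only an average that includes the lingual surfaces. Someone building the eCRF or the analysis could follow either. If the average were chosen, surfaces away from the defect could dilute the treatment contrast. If H3 then failed, HKT, VAS and RES would get no confirmatory test. If the choice stayed open, the outcome for a confirmatory step could be settled after the data are in.

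**Working it through.** **1. The CAL error.** This needs no assumption about effects. Take a site at the entry minimum of RD = 2 mm (5.2.1), fully covered at 12 months (RD = 0), with PD unchanged.
- By the formula in 7.6.7: CAL gain = (PD + 2) − (PD + 0) = 2 mm.
- By a summary formed from PD values: change = PD − PD = 0 mm.

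The two statements in 7.6.7 cannot both describe CAL.

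**2. What the protocol gives for sizing H3.** It gives no effect, SD or inter-site correlation for CAL or PD. Its only sample-size figure is 15 evaluable patients per group for complete root coverage (80% versus 33%, two-sided alpha 0.05, 80% power; 5.2.3). For those inputs the unpooled normal formula gives 13.5, so 14, and the pooled formula gives 17. The stated 15 lies between them and is used below as n.

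**3. Effect of averaging.** Let D be the between-group difference in change at a responding site, s the SD of change per site, ρ the correlation between sites, k = 6 surfaces, and m the number that respond equally.
- Raw effect on the average: D·m/k
- SD of the average: s·√[(1 + (k − 1)ρ)/k]
- Power ≈ Φ(effect / (SD·√(2/n)) − 1.96), with n = 15

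Example with assumed D = 1.0 mm and s = 0.8 mm, where √(2/15) = 0.365:
- Mid-buccal site alone: 1.0/(0.8 × 0.365) = 3.42; 3.42 − 1.96 = 1.46; power 93%.
- Average, m = 1, ρ = 0: effect 1/6 = 0.167 mm, SD 0.8/√6 = 0.327 mm; power 29%.
- Average, m = 3, ρ = 0.3: effect 3/6 = 0.5 mm, SD 0.8·√(2.5/6) = 0.516 mm; power 76%.

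Power over a range of assumed values (ρ = 0 / 0.3 / 0.6 in the last two columns):

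| D (mm) | s (mm) | Mid-buccal site | Average, 1 surface responds | Average, 3 buccal surfaces respond |
|---|---|---|---|---|
| 1.0 | 0.8 | 93% | 29 / 14 / 10% | 99 / 76 / 55% |
| 1.0 | 1.0 | 78% | 20 / 11 / 8% | 92 / 56 / 39% |
| 0.5 | 0.8 | 40% | 10 / 7 / 5% | 55 / 26 / 18% |
| 0.5 | 1.0 | 28% | 8 / 5 / 5% | 39 / 18 / 13% |

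**4. Reading the table.** With one responding surface, the standardised effect falls to 41%, 26% or 20% of its site-level value for ρ = 0, 0.3 or 0.6. With three, the ratio is three times as large: about 122%, 77% or 61%. In that case averaging costs nothing as long as (1 + 5ρ)/6 ≤ (1/2)², that is, ρ ≤ 0.1.

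**The case against.** The wording in 7.6.5 and 7.6.7 is permissive. It says that an average can be calculated, not that the average is the H3 outcome. The stent groove and the reference to control sites support a site-level reading. Six-surface charting also has another use: bleeding on probing is recorded together with PD (7.6.6), and 4.2 monitors bleeding without formal testing. An SAP that is not shown here could fix the unit of analysis. All of this stands, so the finding is an unresolved site, not a wrong outcome already chosen.

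A reader might go further and infer that the H3 contrast nearly vanishes because five of six surfaces cannot respond. The documents do not support that. Section 7.4 extends the graft 3 mm mesial and distal to the exposed root and de-epithelialises the papillae, so the adjacent buccal readings could change.

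A reader might also take the average to run over the whole mouth. With an assumed 28 teeth, 1.0 mm would become 1/168 = 0.006 mm. No section makes a whole-mouth mean the H3 outcome.

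Nor can it be said that the average would block HKT, VAS and RES. That requires H2 to succeed, the average to be adopted, and H3 to fail on the average where it would have passed at the site. With entry PD limited to 4 mm, nothing in the protocol shows that a site-level PD contrast would pass either.

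The reference to PD values in 7.6.7 is probably carried over from 7.6.5, since the correct formula follows it. It still needs correcting. The probe discrepancy is a separate matter and adds no weight to the averaging question. The two probe names may denote one instrument, but the protocol does not say so.

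**Conclusion.** The point holds in a limited form. The CAL summary in 7.6.7 contradicts the formula in the same section, and this rests on no assumption. The site at which H3 is measured is unresolved, because the only stated summary is an average over all surfaces while three other features of the protocol point to the treated mid-buccal site.

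Dilution is conditional on the average being used. Its size cannot be derived from the protocol. Under assumed values it ranges from severe (one sixth of the raw effect left if only one surface responds) to small or absent (half left if all three buccal surfaces respond and correlation is low). The power figures rest on assumed D, s and ρ, equal SDs across surfaces, a normal approximation and 15 per group.

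This should be corrected: H3 is a confirmatory step, and the reading needed to settle it is already among those collected.

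**What to change.** - In 5.1.1.2 and 4.4.1, state that CAL gain and PD reduction for H3 are the change from baseline to 12 months at the mid-buccal site of the treated tooth, read at the stent groove.
- In 7.6.7, compute CAL at that site as PD plus RD, and replace the reference to PD values with CAL values.
- State that any all-surface average is descriptive only.
- Separately, reconcile the probe for RD and the primary endpoint (5.1.1.1 with 7.6.3) and the probe for PD and CAL (7.6 with 7.6.5 and 7.6.7). State one instrument and one reading resolution for each measure. If two names mean the same probe, say so.

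The cost is protocol and eCRF wording. The mid-buccal surface is already measured, so no further examination is needed.
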